### 6.3 Digital radiation therapy data submission using Transfer of Images and Data (TRIAD)

Transfer of Images and Data (TRIAD) is the American College of Radiology's (ACR) image exchange application. TRIAD provides sites participating in clinical trials a secure method to transmit images. TRIAD anonymizes and validates the images as they are transferred.

### **6.3.1** TRIAD Access Requirements

- A valid CTEP-IAM account.
- Registration and Credential Repository (RCR) registration type of: Associate (A), Associate Plus (AP), Non-Physician Investigator (NPIVR), or Investigator (IVR) registration type. Refer to the CTEP Registration Procedures section for instructions on how to request a CTEP-IAM account and complete registration in RCR.
- TRIAD Site User role on an NCTN or ETCTN roster.

All individuals on the Imaging and Radiation Oncology Core provider roster have access to TRIAD and may submit images for credentialing purposes, or for enrollments to which the provider is linked in OPEN.

### **6.3.2 TRIAD Installations**

To submit images, the individual holding the TRIAD Site User role will need to install the TRIAD application on their workstation. TRIAD installation documentation is available at

This process can be done in parallel to obtaining your CTEP-IAM account and RCR registration.

For questions, contact TRIAD Technical Support staff via email

### 6.3.3 Procedures for Data Submission via TRIAD

Radiation therapy treatment plan digital data must include CT scans, structures, plan, and dose files. This study uses TRIAD for submission of RT data. Use of TRIAD requires several preliminary steps as described in Section 6.3.1 and 6.3.2..

Additional information is available at:

### 6.4 Submission of photographs for assessment of acute and chronic toxicities

Photographs of the chest wall will be captured utilizing standardized views (Appendix III). Baseline photographs will be obtained **from all patients** prior to the start of radiation, irrespective of the randomization arm. **For patients randomized to receive Mepitel Film,** baseline photographs will need to be acquired prior to the placement of Mepitel Film. After completion of radiation, two additional sets of photographs will be obtained; one prior to the removal of Mepitel Film, and the second at least one hour after the removal of the Mepitel Film. Photographs for assessment of acute and chronic toxicities will also be obtained at all follow-up time points: 7-14 days post treatment, 3 months, 6 months, 1 year and 2 years post-treatment.

The photographs should be in an image format, such as .jpg. Scanned photographs will not be accepted. See Section 11.3 and Appendix III for photography instructions.

Deidentified photographs will be submitted via email to Please put the protocol number and patient's study ID in the subject line of the email. Alternatively,

photographs can be submitted via TRIAD. See Section 6.3 for instructions for submission via TRIAD.

### 7.0 TREATMENT PLAN/INTERVENTION

### Protocol treatment is to begin $\leq 6$ weeks of registration.

For questions regarding treatment, please see the study contacts page.

Radiation therapy may begin no sooner than 21 days after surgery, or 14 days after the completion of chemotherapy.

**Chemotherapy** is defined as cytotoxic chemotherapy, not biological therapy, such as trastuzumab, pertuzumab, etc.

**Randomization:** Patients will be randomized to either standard of care, or Mepitel Film. Patients receiving standard of care will receive skin care according to their institutional standard of care, as directed by their treating provider. Patients randomized to Mepitel Film, will have Mepitel Film applied to the skin within the radiation treatment field for the duration of radiation therapy.

Schedule deviations of  $\leq +/-1$  day of schedule will not be considered a protocol violation.

**Protocol Summary:** Protocol therapy will consist of conventionally fractionated photon-based post mastectomy radiation therapy +/- a standard radiation boost, and +/- tissue equivalent bolus. Skin management will be randomized between the institutional standard of care, or Mepitel Film, which is a clear, thin, adhesive barrier that will be applied to the skin within the treatment field throughout the duration of radiation therapy.

### 7.1 Surgical Management

Patients are required to have undergone mastectomy, which includes a total, simple, skin sparing, nipple sparing, or modified radical mastectomy. Mastectomy may be conducted at a non-registering institution. Patients with or without reconstruction are allowed to participate in this trial. This includes immediate or delayed reconstruction, including placement of tissue expanders, allograft, saline, silicone, or autologous tissue flap. This protocol does not stipulate lymph node management, though they should be evaluated and treated according to standard of care, which may be conducted at a non-registering institution. Patients will be recorded as having undergone a sentinel node only procedure or axillary dissection. A sentinel node procedure will be considered an axillary dissection if more than 5 lymph nodes are removed. Positive margins are allowed on this study, though the extent and location should be provided.

### 7.2 Mepitel Film/standard of care treatment

Patients will be randomized in a 2:1 ratio to receive either Mepitel Film, or the existing institutional standard of care throughout the duration of their radiation. Radiation and protocol directed skin care (standard of care vs Mepitel Film) will be conducted at the registering institution.

### 7.2.1 Institutional Standard of Care Arm

Patients randomized to the standard of care arm will commence with conventionally fractionated PMRT, with skin management according to their institutional standard of care. Currently, there is no clear standard of care for reducing radiation dermatitis, and clinical practice varies widely across institutions. Patients randomized to this arm, should receive skin management as recommended by their treating physician. To help increase uniformity in the institutional standard of care arm, recommended guidelines for skin care are provided in Appendix IX. We recommend following these guidelines; however, it is not required for participation on this study. Specific skin care products will not be provided for the standard of care arm. Common interventions such as aqueous creams, petroleum ointments, aloe vera, acetic acid soaks, prescription interventions such as mometasone or lidocaine, and

wound care interventions such as Xeroform gauze or silvadene are all permitted. All products used throughout treatment will be recorded for future analyses (Appendix IV). The use of any applied prophylactic barriers including, but not limited to Mepitel Film, Mepitel One, Tegaderm, or Cavilon no sting Barrier Film, is prohibited on this trial. Therapeutic barrier interventions, such as Xeroform, are permitted to treat moist desquamation.

Acquisition of photographs is required for all patients and skin swabs (only for those who provide consent to participate in the optional sub-study). Both initial photos for all patients and skin swabs (for those who consent to participate in the optional correlative substudy) should be acquired no more than 3 days prior to the start of radiation therapy. Immediately upon completion of radiation therapy, the first set of post-treatment photographs and the second set of skin swabs should be acquired.

### 7.2.2 Mepitel Film Arm

Patients randomized to the Mepitel Film arm will have Mepitel Film applied to the breast/chest wall prior to starting radiation therapy and changed as needed throughout treatment with a minimum frequency of once every two weeks. The Thin Film Clinical Utilization Survey must be completed once per week prior to radiation treatment (Appendix VIII). Mepitel Film should be replaced if it peels to the point that it compromises the intended skin coverage or becomes loosely adhesive during treatment. An initial generous application of Mepitel Film can allow one to trim edges off as they peel without compromising coverage. Additionally, if only a small piece of the Mepitel Film falls off, or peels, then a person can replace only the compromised area using a patchwork technique. Importantly, a small piece of Mepitel Film will be applied to the contralateral breast/chest wall as a control. This piece should be changed as needed throughout treatment with a minimum frequency of once every two weeks.

The acquisition of photographs for all patients, and skin swabs (only for those who provide consent to participate in the optional sub-study) requires coordination with the planned placement of Mepitel Film. The initial photographs and skin swabs are acquired prior to the first application of Mepitel Film. Both initial photos for all patients and skin swabs (for those who consent to participate in the optional correlative substudy) should be acquired no more than 3 days prior to the start of radiation therapy. Mepitel Film should then be applied to the entire breast/chest wall and changed as needed throughout treatment. Upon completion of radiation the first set of post-treatment photographs should be acquired. The Mepitel Film should then be removed, and the second set of skin swabs should be acquired immediately following removal of the Mepitel Film. A minimum of one hour should pass following removal of Mepitel Film, to allow for transient erythema to resolve, before a second set of post-treatment photographs is acquired. After this second set of photographs, Mepitel Film should be reapplied to the breast/chest wall. Given radiation dermatitis can often peak in the 1-2 weeks post-treatment, this final application of Mepitel Film continues to be protective. It should be communicated to the patient, that she can allow this final layer of Mepitel Film to peel off naturally.

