# Preparing for swab collection and Mepitel Film application for patients on the Mepitel Film arm:

- **3.** Make sure to review which side will be receiving treatment (right vs left). Review patient randomization to confirm patient is randomized to receive Mepitel Film. Please see Appendix X and follow instructions during collection of skin swabs, and Mepitel Film application.
- 4. Mark the skin with non-permanent marker to outline area where the Mepitel Film will be placed. These marks will help ensure the swabs are collected from the

correct areas of skin. Mark the contralateral breast/ chest wall where the small control square of Mepitel Film will be placed.

**5.** Collect swabs as directed in Appendix X.

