# 9.2 CTCAE Routine Reporting Requirements

In addition to the solicited adverse events listed in Section 9.1, the following table outlines the combinations of time points, grades and attributions of AEs that require routine reporting to the Alliance Statistics and Data Center. Questions about routine reporting should be directed to the Data Manager.

Combinations of CTCAE Grade & Attribution Required for Routine AE Data Submission on Case Report Forms (CRFs). Attribution may be secondary to radiation, and/or Mepitel Film.

Of note, pruritus is a common acute toxicity observed secondary to radiation and can also develop in response to Mepitel Film. Based on Mayo institutional experience, pruritus due to Mepitel Film is generally seen within the first week of use.

Attribution	Grade 1	Grade 2	Grade 3	Grade 4	Grade 5
Unrelated			a	a	a
Unlikely			a	a	a
Possible		a	a, b	a, b	a, b
Probable		a	a, b	a, b	a, b
Definite		a	a, b	a, b	a, b

- a) Acute Adverse Events: Other CRF Applies to AEs occurring between registration and within 90 days of the patient's last treatment date, or as part of the Clinical Follow-Up Phase.
- b) Chronic Adverse Events: Late CRF Applies to AEs occurring greater than 90 days after the patient's last treatment date.

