# 11.2 Site staff survey: Thin Film Clinical Utilization Survey (Appendix VIII)

This survey is not a validated metric but has been designed as a quick method for trained staff to track and record their experience in working with Mepitel Film (see Section 1.6). The survey tracks the frequency of film exchange, quantity of film used, incidence of film detachment, time and number of personnel required for exchange, and ease of use, allowing for descriptive reporting of these parameters. This survey should be completed once per week, prior to radiation therapy. It will take approximately 5 minutes to complete this survey. Recognizing that the application of Mepitel Film requires nursing/trained staff support, demonstration of its feasibility and ease of use will provide valuable data regarding its feasibility and generalizability. Furthermore, tracking the quantity of Mepitel Film used across patients will allow for an estimation of the average financial cost of this intervention.

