# 14.2.2 Objectives

- a) To determine the impact of ionizing radiation on the skin microbiome, including quantitative analysis of *S. aureus*.
- b) To determine the effect of Mepitel Film on the skin microbiome, including quantitative analysis of *S. aureus*.
- c) To determine the impact of Mepitel Film on radiation-induced changes in the skin microbiome, including quantitative analysis of *S. aureus*.

d) To correlate the aforementioned alterations in the skin microbiome with the observed severity of radiation dermatitis.

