# APPENDIX VII NCI PRO-CTCAE ITEM ™ ENGLISH Item Library version 1.0

Rarely

Mild

A little bit

As individuals go through treatment for their cancer they sometimes experience different symptoms and side effects. For each question, please check or mark an  $\boxtimes$  in the one box that best describes your experiences over the past 7 days.

PR	PRO-CTCAE ™ Symptom Term: Radiation skin reaction							
1.	In the last 7 days, what was the SEVERITY of your SKIN BURNS FROM RADIATION at their WORST?							
	o None	o Mild	
 
Moderate
 
	o Severe	

Very severe

	

Not applicable

		
PR	PRO-CTCAE™ Symptom Term: Itching							
2.	. In the last 7 days, what was the SEVERITY of your ITCHY SKIN at its WORST?							
	o None	o Mild	o Moderate	o Severe	e O Very sev	ere		
PR	O-CTCAE™ Sym	ptom Ter	m: General pa	ain				
3.	In the last 7 day	s, how O	FTEN did you	have PAIN?				

The PRO-CTCAE™ items and information herein were developed by the NATIONAL CANCER INSTITUTE at the NATIONAL INSTITUTES OF HEALTH, in Bethesda, Maryland, U.S.A. Use of the PRO-CTCAE™ is subject to NCI's Terms of Use

Moderate

Somewhat

In the last 7 days, how much did PAIN INTERFERE with your usual or daily

In the last 7 days, what was the SEVERITY of your PAIN at its WORST?

Occasionally
 Frequently

Severe

Quite a bit

Never

None

Not at all

Almost

constant

Very severe

Very much

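### Every film-arm patient wears a contralateral control film that only the optional swab sub-study uses, and the film-use survey, as far as it can be read, does not separate it from the intervention

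*Combined protocol and SAP*

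**What the plan says.** Section 7.2.2 (Mepitel Film Arm) says: "Importantly, a small piece of Mepitel Film will be applied to the contralateral breast/chest wall as a control". It continues: "This piece should be changed as needed throughout treatment with a minimum frequency of once every two weeks". Neither sentence mentions sub-study consent, although the next paragraph of that section limits skin swabs to patients who consent to the optional sub-study.

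Section 7.0 defines the intervention more narrowly: "Patients randomized to Mepitel Film, will have Mepitel Film applied to the skin within the radiation treatment field for the duration of radiation therapy".

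The contralateral piece has one documented use. The film-arm swab steps in section 6.2.2 say: "Mark the contralateral breast/ chest wall where the small control square of Mepitel Film will be placed". This fits objective (b) of the sub-study in section 14.2.2: "To determine the effect of Mepitel Film on the skin microbiome, including quantitative analysis of" S. aureus. Sections 4.5.1 and 6.2 make participation in the sub-study optional. Elsewhere the piece appears only as a placement tip in the step-by-step instructions of 7.2.2. No endpoint or analysis in section 13 refers to it.

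These outcomes could pick the piece up:

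- **Film use and cost (objective 2.3.3).** Section 11.2 says that "tracking the quantity of Mepitel Film used across patients will allow for an estimation of the average financial cost of this intervention". Appendix VIII asks for the pieces used by size and for the minutes and personnel needed.
- **PRO-CTCAE itch (Appendix VII).** The item reads "In the last 7 days, what was the SEVERITY of your ITCHY SKIN at its WORST".
- **CTCAE skin events (sections 9.1 and 9.2).** Pruritus, rash and skin infection are solicited without a body site. Section 9.2 notes that "pruritus is a common acute toxicity observed secondary to radiation and can also develop in response to Mepitel Film".
- **Stopping rule (section 13.8.3).** It counts grade 3 or higher events at least possibly related to film, again with no site.

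**The concern.** The film arm receives something that the definition in section 7.0 does not include: film on skin that is not irradiated, worn for the whole course of radiation. The standard-of-care arm has no counterpart.

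For ST1 participants the piece has a purpose. For those who decline, it is an adhesive exposure with no documented use.

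It can also leak into results meant to describe the intervention. Film quantity, staff time and cost are what a clinic would use to decide on adoption, and no clinic would apply the contralateral piece in practice. Itch or rash on that side could be recorded as a film-arm event, because the text shown asks for no site. Any such leakage counts against film.

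**Working it through.** **1. Does it reach the primary endpoint?** The documents give no figure for the contralateral film. The nearest is the primary power in section 13.3: at least 90% with 128 and 64 patients, effect size 0.5 and two-sided 5%.

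- Noncentrality: 0.5 / √(1/64 + 1/128) = 3.27.
- Power by normal approximation: 90.4% at 0.05 and 90.3% at 0.049.
- With both looks (0.003 and 0.049, interim at half the information): 90.3%, with overall alpha 0.0500.

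The stated power reproduces. In Appendix VI the pain, itch and burning items each name the treatment area. The fourth item, on daily activities, names no site but asks about the skin reaction and its symptoms. The provider scale rates the desquamation and necrosis items by the proportion of the treatment area affected. The primary score and its power are therefore not directly affected.

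**2. How many patients wear the piece without a documented use?** The film arm is planned at 144 (section 13.3). The number is 144 × (1 − uptake of ST1). The documents give no uptake. Assuming 80%, 144 × 0.2 ≈ 29; assuming 50%, 144 × 0.5 = 72.

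**3. How much film does it add?** Let A be the area of the contralateral piece, T the treated-side area per change, and f the contralateral change frequency relative to the treated side. Added film = f × A / T.

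- A: the 7.2.2 instructions describe one uncut small piece. Section 10.1 restricts the study to 10 x 25 cm (250 cm²) and 15 x 20 cm (300 cm²), but Appendix VIII also has a row for 10 x 12 cm (120 cm²). The documents disagree on the sizes in use.
- T: not given. Assumed 2 to 4 sheets of 15 x 20 cm, that is 600 to 1200 cm².
- f: not given. Section 7.2.2 sets the same two-week minimum for both sides. Section 15.2 expects re-application about weekly, and 7.2.2 ties treated-side replacement to peeling and lost adhesion. I show f = 1 and f = 0.5 (treated side weekly, contralateral piece at its two-week minimum).

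| Piece | f = 1 | f = 0.5 |
|---|---|---|
| 10 x 12 cm | 120/1200 to 120/600 = 10–20% | 5–10% |
| 10 x 25 cm | 250/1200 to 250/600 = 21–42% | 10–21% |

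Staff time is recorded in the same survey, but the documents give no basis for sizing that part.

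**4. Itch, rash and the stopping rule.**

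- Sections 13.5.2 and 13.6.2 summarise CTCAE and PRO-CTCAE events by each patient's maximum grade. A contralateral reaction changes a patient's entry only if it is worse than anything on the irradiated, film-covered side.
- Section 7.2.2 puts film intolerance below 10% of patients. That is intolerance overall, not reactions confined to the contralateral side, so it does not size this effect.
- The stopping rule looks at the first 27 patients, about 27 × 2/3 = 18 of them on film. It suspends accrual at 3 or more events if the percentage is higher with film. A contralateral event could count, but its probability cannot be computed from the documents.

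**The case against.** The strongest reply is that little of importance is touched. The primary items name the treatment area. The acute event, PRO-CTCAE and utilisation results are descriptive, with no between-arm test planned. Any bias runs against film, and a film-intolerant patient would probably react on the treated side too. All of this stands, and it keeps the point modest.

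Three stronger readings are tempting but unsupported:

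- **That the film arm's itch results are biased in general.** The mRISRAS itch item is limited to the treatment area. Only the PRO-CTCAE item and the CTCAE terms are open as to site, and the excess there is unknown and probably small.
- **That the piece must be at least 250 cm².** This follows from section 10.1 alone. Appendix VIII lists 10 x 12 cm, and section 6.2.2 describes a small square, which 10 x 25 cm is not. If the piece is 10 x 12 cm, the survey's row for that size might largely isolate it, although minutes would remain pooled.
- **That the data certainly cannot separate the sides.** The case report forms are not in the document, and the survey's instruction line is broken in the text available. Either may already restrict or record the side.

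It can also be argued that film on non-irradiated skin helps providers tell film intolerance from radiation effect (sections 7.2.2 and 9.2). That is possible, but the documents do not state this use and no analysis relies on it.

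**Conclusion.** The point holds in a limited form. Section 7.2.2 gives the contralateral film to the whole film arm, while its only documented use is an optional sub-study. For those who decline, the exposure serves no stated analysis.

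The most certain consequence is for objective 2.3.3: unless the survey's unreadable line or the data forms already separate the piece, film quantity, staff time and cost are overstated. The added film area runs from about 5% (10 x 12 cm, changed half as often) to about 42% (10 x 25 cm, changed equally often). All of these figures rest on the assumed 600 to 1200 cm² of treated-side film per change.

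The effect on the CTCAE pruritus and rash tables, PRO-CTCAE itch and the stopping rule is possible, unfavourable to film and unquantified. The primary result is not directly affected.

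**What to change.** - **Section 7.2.2:** limit the contralateral piece to film-arm patients registered to A221803-ST1.
- **Appendix VIII:** count treated-side film and minutes separately from the ST1 control piece, and base the cost estimate in 2.3.3 and 11.2 on the treated side. This is needed as well as the consent link, because ST1 participants will still wear the piece.
- **Adverse event form:** record whether pruritus, rash or skin infection is inside or outside the treatment field, if the form does not already do so.
- **Sections 10.1 and Appendix VIII:** reconcile the film sizes.

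Comparing itch and rash by ST1 participation would not substitute for recording the site, because those groups are self-selected.

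The cost is a sentence in 7.2.2, one survey line and possibly one case report form field. ST1 loses no data, and patients who decline it avoid an unused exposure.
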